Study Protocol: Effectiveness and safety of Bictegravir/emtricitabine/tenofovir alafenamide (B/F/TAF) in HIV-1 infected patients with Active illicit Substance use (BASE)

Investigators: [name], [name], [name], [name], [name], [name]

NCT: 03998176

Hypothesis: People living with HIV (PWH) that use illicit substances receiving B/F/TAF will have virologic suppression similar to PWH that do not use illicit substances receiving B/F/TAF without safety concerns or treatment emergent resistance

Abstract:

Description:

Illicit substance use is a growing concern across the United States and has been linked to HIV outbreaks and viral hepatitis. Close to half of people living with HIV (PWH) struggle with a substance use disorder often leading to non-adherence of antiretroviral therapy (ART) increasing the risk of poor treatment outcomes and potential HIV transmission. Appropriate choice of ART for PWH who use illicit substances is unknown. Boosted protease inhibitor regimens are utilized for their high genetic barrier to resistance, however, concerns for drug-drug interactions with illicit substances are present. The clinical utility of an integrase strand inhibitor (INI) based regimen is unknown. We aim to assess the effectiveness and safety of bictegravir/emtricitabine/tenofovir alafenamide in PWH who actively use illicit substances.

Eligibility:

Eligible participants for the study will be HIV-1 infected patients at the Specialty Care Center with HIV viremia > 1000 copies/mL and ongoing substance use by urine drug screen or self-reported within 6 months. Participants must also have a creatinine clearance of 30 mL/min or greater, no tenofovir or INI HIV resistance mutations, and not be pregnant. Illicit substances will include: methamphetamine, heroin, cocaine, PCP, GHB, ketamine, or inappropriate benzodiazepine, prescription opiate, or prescription stimulant usage.

Interventions/Evaluations:

This is a single-center, single-arm, prospective, pilot study to evaluate the effectiveness and safety of B/F/TAF in PWH and active illicit substance use. We aim to evaluate the proportion of patients at week 24 with undetectable viral loads (<50 copies/mL). We plan to enroll 45 participants.

Secondary/exploratory endpoints include the proportion with undetectable viral loads at week 48, proportion with emergent drug resistance, change in CD4 counts, and evaluation retention in care. Substance use throughout the study will be evaluated by the NIDA Modified-ASSIST questionnaire. Adherence will be evaluated by refill history/percentage of days covered, ACTG Self-Report Adherence questionnaire, and FTC-TP and TDF-DP levels by dried blood spots.

Follow-up:

Participants will be followed up at weeks 6, 12, 24, 36, and 48. Participants will be compensated for visits completed at \$20 per hour.

Brief Description: Illicit substance use in the United States is a growing concern across all states. Use of illicit drugs such as cocaine, heroin, methamphetamine, prescription opioids and stimulants, and 3,4-methylenedioxy-methamphetamine (Ecstasy, MDMA) among others, has remained steady in many parts of the United States [1]. In 2017, 6% of new HIV infections occurred in people who injected drugs and 3% were in gay/bisexual men who injected drugs [2]. Furthermore, injection of illicit drugs has been linked to outbreaks of HIV and viral hepatitis acquisition [3].

Of the 1.2 million PWH in the US, an estimated 48% struggles with a substance use disorder [4]. Poor antiretroviral treatment (ART) adherence and inconsistencies in retention in HIV care has been observed among PWH that use illicit drugs. Gaps in ART coverage and lack of retention to HIV care are factors that complicate successfully managing PWH who use illicit drugs, often leading to poor treatment outcomes and increased HIV transmission [5-7]. As a result, ART choice in these patients can prove challenging and often requires the selection of an ART regimen with a high genetic barrier to resistance such as protease inhibitor based ART [8-10]. Yet, concerns of drug-drug interactions between illicit drugs and ART regimens containing a protease inhibitor and/or a pharmacokinetic enhancer have been raised [11,12]. Integrase strand inhibitor (INSTI) based ART regimens are now the primary treatment option for most PLWH in the US [8]. B/F/TAF is the newest INSTI based regimen available as a generally well-tolerated, single tablet formulation that does not require the need for a pharmacokinetic enhancer and is thought to provide a high genetic barrier to resistance. In clinical trials among naïve and treatment experienced, virologically suppressed patients, B/F/TAF exhibited efficacy of 89% to 96% without any cases of newly emergent treatment resistance [13-16].

However, little is known about the effectiveness and safety of B/F/TAF in PWH who actively use illicit drugs because such patients are typically excluded from clinical trials. In this study, we aim to evaluate the effectiveness and safety of B/F/TAF among viremic patients currently using illicit drugs at the Nebraska Medicine, Specialty Care Center (SCC) in Omaha, NE.

The SCC clinic manages approximately 1300 PLWH's HIV care of which 89% is actively engaged in care. An estimated 8% to 12% of SCC's patients uses some form of illicit substance excluding nicotine, alcohol, or marijuana on a semi-regular basis.

Objectives:

[figure not shown]
1. *Primary*
 - a. To evaluate the virologic suppression of PLWH with ongoing illicit substance use receiving B/F/TAF
2. *Secondary*
 - a. Evaluate the safety of B/F/TAF in PLWH with ongoing illicit substance use
3. *Exploratory*
 - a. Evaluate for the development of treatment emergent resistance in PLWH on B/F/TAF with ongoing illicit substance use
 - b. To evaluate the change in CD4 after starting B/F/TAF in PLWH with ongoing illicit substance use
 - c. Evaluate the retention in care of PLWH on B/F/TAF with ongoing illicit substance use
 - d. Evaluate the medication adherence of PLWH on B/F/TAF with ongoing illicit substance use

Endpoints:

1. *Primary*

- a. Proportion of participants with ongoing illicit substance use on B/F/TAF with HIV RNA <50 copies/mL at week 24 by FDA Snapshot Algorithm
- 2. *Secondary*
 - a. Proportion of participants who experience adverse events (grade 3 or above) at week 24 and 48
- 3. *Exploratory*
 - a. Proportion of participants with HIV RNA <50 copies/mL at week 48 by FDA Snapshot Algorithm
 - i. Reported as demographics, intention to treat, and per-protocol
 - b. Proportion of participants with HIV RNA <50 copies/mL at week 48 by FDA snapshot algorithm adjusted by type of illicit substance use
 - c. Proportion of participants with treatment emergent resistance at week 24 and 48
 - d. Change in CD4 at week 24 and 48 from baseline
 - e. Proportion of participants completing follow-up visits through weeks 24 and 48
 - i. Calculated as completed study visits/total number of study visits.
 - f. Adherence assessment
 - i. Adherence measure
 - 1. Self-reported adherence questionnaire
 - 2. Pill counts/PDC
 - ii. Tenofovir Pharmacokinetic Sampling
 - 1. TDF-DP and FTC-TP via DBS

Study Design: Prospective, single arm, open-label, pilot study

1. Documented HIV infection
2. ≥ 19 years old
3. Self-reported illicit substance use or confirmed by urine drug screen within past 6 months
 - a. Cocaine
 - b. Heroin
 - c. Methamphetamine
 - d. PCP/ketamine/GHB
 - e. Opiates
 - f. Inappropriate use of prescription pills (opiates/benzodiazepines/stimulants) regardless of prescription
4. HIV RNA $\geq 1,000$ copies/mL not presently taking B/F/TAF

5. Any CD4 count
6. Creatinine clearance >30 mL/min (Cockcroft-Gault)
7. ALT and AST < 5 times the upper limit of normal
8. Willing and able to give written informed consent

Exclusion Criteria:

1. History of INI or TAF-related resistance mutations as defined by the IAS-USA
2. Pregnancy
3. Any concomitant use of dofetilide or known medications to reduce systemic exposure to B/F/TAF (i.e. rifamycins, carbamazepine, St. John's Wort)
4. Serious illness requiring systemic treatment (i.e. prolong intravenous treatment such as chemotherapy, extended antibiotic therapy, etc) and/or hospitalization within 30 days prior to entry

Methods:

After obtaining written informed consent, prospective participants will be screened with a clinical assessment (physical exam), laboratory testing (CBC, CMET, HBV/HCV serology, CD4, HIV RNA), and substance use evaluation (NIDA ASSIST) to evaluate study eligibility. Eligible patients may initiate treatment with B/F/TAF on the same day as the screening visit or start within 30 days of screening.

Post-entry evaluations will occur at weeks 6, 12 and 24, 36, and 48. Clinical and safety laboratory monitoring including blood chemistries, plasma HIV RNA levels, CD4 counts and blood sampling for ART drug quantification will take place at week 6, 24, and 48 weeks. Pregnancy testing will be performed any time pregnancy is suspected. Assessment of adverse events, adherence, ongoing substance use, and quality of life will be assessed at each visit. Adherence measures include pill counts, self-reported by visual analog scale by the ACTG Brief Adherence Self Report [17] and pharmacokinetic sampling (see below). Ongoing illicit substance use will be evaluated quarterly at week 12, 24, 36, and 48 through the NIDA ASSIST [18]. Referral for substance use counseling and/or outpatient or inpatient treatment will be offered. Additionally, the Short Form 12 survey will be utilized to evaluate quality of life and patient reported outcomes [19-21]. See schedule of events table for detail.

Virologic Failure:

Suspected virologic failure will be defined as plasma HIV RNA > 400 copies/mL after week 12 and will be confirmed by a repeat measurement within 28 days. Participants with confirmed virologic failure will undergo genotype resistance testing using the Genosure Prime assay. Participants with emergent INI or TAF related HIV drug resistance development will undergo ART revision but will continue to be followed on study.

Adverse Events:

Signs and symptoms will be graded according to the DAIDS Table for Grading the Severity of Adult and Pediatric Adverse Events [22]. All signs and symptoms grade 3 or above or any grade that led to treatment discontinuation, will be recorded on study case report forms and tracked in the REDCap data management

Pharmacokinetic Sampling:

Blood for PK studies will be collected at three time points while on study, week 6, 24 and 48. 4mL of K2 EDTA whole blood will be collected via venipuncture for tenofovir-diphosphate (TDF-DP) and

emtricitabine-triphosphate (FTC-TP) determination at each of the three study visits. Using a Whatman 903 Protein Saver card (DBS card), 25 microliters of whole blood from the K2 EDTA will be spotted on each circle on the card and allowed to dry for at least 3 hours. Dried DBS cards will be stored at -80°C in plastic bags until analysis. TDF-DP and FTC-TP will be quantified from the DBS card using a 3 mm punch and LC-MS/MS [23-25]. TDF-DP and FTC-TP represent different elimination half-lives (TDF-DP: long-term - 17 days vs. FTC-TP: short-term - 35 hours), drug concentration data obtained at these three time points will help provide a collective, objective measurement of ART adherence both recent and longitudinally.

Patient Compensation:

Patients will receive a preloaded gift card for visit completion at a rate of \$20 per hour. The anticipated time of visits is 4 hours for the first visit and 2 hours for each subsequent visit.

Visit Spacing:

Visit windows for the study will be +/- 3 weeks for the week 6 visit, +/- 4 weeks for the week 12 visit, and +/- 6 weeks for the weeks 24, 36, and 48 study visits.

Data Management:

All data collected from study visits will be kept in REDCap, a HIPPA secure database hosted by the University of Nebraska Medical Center. Questionnaires throughout the study will also be imported into REDCap.

Study Monitoring/Safety/Futility:

An investigational monitoring committee (IMC) comprised of an HIV clinician and HIV pharmacologist along with the study team statistician will evaluate study safety, recruitment, and futility twice throughout the course of the study. The first time point for IMC review will occur after the first 15 participants reach week 24 and with the second time point at end of study enrollment.

Additionally, the study team will perform internal audits annually to ensure all data is correctly input in the data management system, REDCap, and to ensure that all study procedures are being performed as planned.

Should a female participant become pregnant during the course of the study, they will be approached about enrollment in the Antiretroviral Pregnancy Registry. The participant will be taken off B/F/TAF and changed to a preferred Department of Health and Human Services recommended ART for use during pregnancy. A referral to obstetrics will additionally be placed and they will continue to follow on study until completion.

Schedule of Procedures:

See Addendum A

Questionnaires:

See Addendum's B-C

Study Follow-up/Labs:

Intervention Type	Entry/WK0	WK6	WK12	WK24	WK36	WK48
Laboratory	CBC/CMET HIV RNA CD4 HBV/HCV serologies Urine Pregnancy	CMET HIV RNA Urine Pregnancy	Urine Pregnancy	CBC/ CMET HIV RNA CD4 Urine Pregnancy	Urine Pregnancy	CBC/ CMET HIV RNA CD4 Urine Pregnancy
Safety		X	X	X	X	X
Adherence Questionnaire		X	X	X	X	X
Substance use Questionnaire	X		X	X	X	X
PRO Questionnaire	X			X		X
PHARMACOKINETIC SAMPLING		X		X		X
Physical Exam	X			X		X

Sample Size Justification:

The sample size justification is based on the estimation of a confidence interval for a single proportion. We are interested in estimating the precision of determining the proportion of PLWH with ongoing illicit substance use on B/F/TAF with HIV RNA <50 copies/mL at week 24. It is proposed that this proportion could range from .60 to .80 depending on how adherent patients are to the therapy. It is also uncertain how many eligible patients will continue on treatment through week 24.

The table below provided estimates of precision (with 95% confidence) based on the number of patients who complete 24 weeks of therapy and the proportion who achieve HIV RNA <50 copies/mL.

Confidence Level	Sample size	CI Width	Proportion HIV RNA <50	Lower limit	Upper limit
0.95	20	0.45	0.6	0.36	0.81
0.95	20	0.42	0.7	0.46	0.88
0.95	20	0.38	0.8	0.56	0.94
0.95	25	0.40	0.6	0.39	0.79
0.95	25	0.38	0.7	0.49	0.87
0.95	25	0.34	0.8	0.59	0.93
0.95	30	0.37	0.6	0.41	0.77
0.95	30	0.35	0.7	0.51	0.85
0.95	30	0.31	0.8	0.61	0.92

0.95	35	0.34	0.6	0.42	0.76
0.95	35	0.32	0.7	0.52	0.84
0.95	35	0.29	0.8	0.63	0.92
0.95	40	0.32	0.6	0.43	0.75
0.95	40	0.30	0.7	0.54	0.83
0.95	40	0.27	0.8	0.64	0.91

This is a pilot study to estimate the efficacy (i.e. HIV RNA <50 copies/mL at week 24) of B/F/TAF in PLWH with ongoing illicit substance usage. A sample size of 30 produces a two-sided 95% confidence interval with a width equal to 0.35 when the sample proportion of patients who achieve HIV RNA <50 copies/mL at week 24 is 0.70. The sample size will be increased to 45 patients to account for an estimated attrition of ~50%.

Data analysis [26, 27]:

Statistical analysis will be performed using GraphPad Prism, SAS as well as IBM SPSS software.

Descriptive summaries will be presented using means, medians, standard deviations, and ranges for continuous variables and frequencies and percentages for categorical variables. Patients achieving HIV RNA <50 copies/mL at week 24 will be presented as a proportion and 95% confidence interval. Counts and percentages will be used to describe safety assessment, retention and adherence of B/F/TAF in HIV infected patients with ongoing illicit substance usage. Adherence will also be evaluated with summary statistics of drug levels measured in patients at the 24 week visit. A logistic regression model may be considered to investigate the effect of adherence on the 24 week outcome.

References

1. Substance Abuse and Mental Health Services Administration (2018). Results from the 2017 National Survey on Drug Use and Health. Rockville, MD: Substance Abuse and Mental Health Services Administration.
2. Centers for Disease Control and Prevention. HIV Surveillance Report, 2017; vol. 29. <http://www.cdc.gov/hiv/library/reports/hiv-surveillance.html>. Published November 2018. Accessed [December 2018].
3. Peters, P.J., et al., *HIV Infection Linked to Injection Use of Oxymorphone in Indiana, 2014-2015*. N Engl J Med, 2016. **375**(3): p. 229-39.
4. Hartzler, B., et al., *Prevalence and Predictors of Substance Use Disorders Among HIV Care Enrollees in the United States*. AIDS Behav, 2017. **21**(4): p. 1138-1148.
5. Meyer, J.P., A.L. Althoff, and F.L. Altice, *Optimizing care for HIV-infected people who use drugs: evidence-based approaches to overcoming healthcare disparities*. Clin Infect Dis, 2013. **57**(9): p. 1309-17.
6. Kamarulzaman, A. and F.L. Altice, *Challenges in managing HIV in people who use drugs*. Curr Opin Infect Dis, 2015. **28**(1): p. 10-6.
7. Shubber, Z., et al., *Patient-Reported Barriers to Adherence to Antiretroviral Therapy: A Systematic Review and Meta-Analysis*. PLoS Med, 2016. **13**(11): p. e1002183.
8. Panel on Antiretroviral Guidelines for Adults and Adolescents. Guidelines for the Use of Antiretroviral Agents in Adults and Adolescents Living with HIV. Department of Health and Human Services. Available at

<http://aidsinfo.nih.gov/contentfiles/lvguidelines/AdultandAdolescentGL.pdf>. Section “What To Start.” [December 2018]. [F-1 – F-42]

9. Dierynck, I., et al., *Binding kinetics of darunavir to human immunodeficiency virus type 1 protease explain the potent antiviral activity and high genetic barrier*. J Virol, 2007. **81**(24): p. 13845-51.

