Race	X					
Ethnicity	X					
Education	X					
Gender	X					
ART Exp	X					
Housing	X					
Income	X					
Reported Illicit Substance or UDS Result	X					
Baseline/Archived Resistance	X					
Clinical Information						
CBC	X			X		X
Creatinine	X	X		X		X
AST	X	X		X		X
ALT	X	X		X		X
HBV c Ab	X					
HBV s Ab	X					
HBV s Ag	X					
HCV Ab	X					
HIV RNA	X	X		X		X
CD4	X			X		X
CD4%	X			X		X
CD4/CD8	X			X		X
Pregnancy (if applicable)	X	X	X	X	X	X
Emergent Resistance		X		X		X
Safety/AE Assessment						
Physical Exam						
	X			X		X

Questionnaire						
ACTG Adherence		X	X	X	X	X
NIDA ASSIST	X		X	X	X	X
SF-12 Survey	X			X		X
Lab Collection						
DBS Card Collection		X		X		X

Addendum B: Adherence Questionnaire – adapted from ACTG Visual Analog Scale

BASE Study: ACTG Adherence

Name:

Visit Week:

DOB:

Participant ID:

Reported Adherence

[figure not shown]
We understand that many people on anti-HIV medications find it very difficult to take them regularly. We would like to know HOW MUCH of your anti-HIV medications you have taken DURING THE LAST MONTH.

Please put a cross (**X**) on the line below at the point showing your best guess about how much of your anti-HIV medication you have taken **in the last month**. We would be surprised if this was 100% for most people.

For example: **0%** means you have taken **none** of your anti-HIV medication.

50% means you have taken **half** your anti-HIV medication.

100% means that you have taken **every single dose** of your anti-HIV medication in the past month.

Self-reported adherence score: _____

Addendum C: Substance Use Questionnaire – adapted from NIDA-ASSIST

BASE Study: NIDA ASSIST

Name: _____ Visit Week: _____
DOB: _____ Participant ID: _____

NIDA Quick Screen:

In the past year, how often have you used the following?

Alcohol	Never	Once or twice	Monthly	Weekly	Daily or Almost Daily
• Men (≥ 5 drinks/day)					
• Women (≥ 4 drinks/day)					
Tobacco Products					
Prescription Drugs for Non-Medical Reasons					
Illegal Drugs					

NIDA Modified Screen:

1. In your lifetime, which of the following substances have you ever used?

Cannabis (marijuana, pot, grass, hash, CBD, etc.)	Yes	No
Cocaine (coke, crack, etc.)		
Prescription stimulants (Ritalin, Concerta, Dexedrine, Adderall, diet pills, etc)		
Methamphetamine (speed, crystal meth, Tina, ice, etc)		
Inhalants (nitrous oxide, glue, gas, paint thinner, "poppers", etc.)		

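### The secondary endpoint counts grade 3 or higher adverse events, but the only grading and recording rule covers signs and symptoms, so symptomless laboratory toxicity has no stated route into it

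*Combined protocol and SAP*

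**What the plan says.** Under Endpoints, the single secondary endpoint is "Proportion of participants who experience adverse events (grade 3 or above) at week 24 and 48".

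The Adverse Events section supplies the only operational rule. On grading: "Signs and symptoms will be graded according to the DAIDS Table for Grading the Severity of Adult and Pediatric Adverse Events". On recording: "All signs and symptoms grade 3 or above or any grade that led to treatment discontinuation, will be recorded", on case report forms and in REDCap.

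The Methods section schedules "Clinical and safety laboratory monitoring including blood chemistries, plasma HIV RNA levels, CD4 counts" and drug-level sampling at weeks 6, 24 and 48. It also states: "Assessment of adverse events, adherence, ongoing substance use, and quality of life will be assessed at each visit". It does not say whether that assessment includes review of laboratory results.

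The Study Follow-up/Labs table has CMET at entry and weeks 6, 24 and 48, and CBC at entry and weeks 24 and 48. Addendum A lists creatinine, AST and ALT at the same times as CMET, under a clinical information heading that is separate from "Safety/AE Assessment". Inclusion criterion 7 is "ALT and AST < 5 times the upper limit of normal". Data Management places all visit data in REDCap. The Data analysis section offers counts and percentages for safety and specifies no laboratory summary.

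**The concern.** The endpoint and the rule that feeds it have different scope. Adverse events is the broader term; signs and symptoms, in ordinary use, are what the participant reports or the examiner finds. A raised creatinine or transaminase in someone who feels well is neither, unless somebody chooses to call it a sign.

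At stake is the only secondary endpoint of a study whose hypothesis includes the absence of safety concerns, in a population for which the protocol itself says little safety evidence exists. If the rule is followed as written, the reported proportion may leave out findings from the tests that the protocol labels as safety monitoring. If it is not, someone must decide after the data are in, in an open-label single-arm study, whether those findings count. Two analysts working from this plan could report different values.

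**Working it through.** The plan gives no expected rate, target or precision for the safety endpoint, so there is no figure to reproduce. The check is mainly one of text.

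**Step 1: scope of each provision.**

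| Provision | Scope as written |
|---|---|
| Secondary endpoint | Adverse events, grade 3 or above |
| Grading rule | Signs and symptoms |
| Recording rule | Signs and symptoms, grade 3 or above, or any grade leading to discontinuation |
| Laboratory schedule | CMET and CBC; the Methods text calls the testing safety monitoring |
| Data Management | All visit data, hence laboratory values too |
| Data analysis | Counts and percentages for safety; no laboratory grading or shift table |

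**Step 2: follow one case through the rule.** Take a participant with no symptoms whose week 24 ALT would be grade 3. The value is drawn and stored. The grading sentence does not reach it. The recording sentence does not reach it either, and its discontinuation clause also attaches to signs and symptoms. No other section turns the stored value into an event. On a literal reading, this participant is not counted.

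**Step 3: baseline abnormalities.** Entry allows ALT and AST up to just under 5 times the upper limit of normal. Some participants may therefore start with raised values, and the plan has no rule separating these from on-treatment changes. Grading without such a rule could count abnormalities already present at entry.

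**Step 4: what each missed participant is worth.** With the planned enrolment of 45 as denominator, k participants whose only grade 3 or higher event is a laboratory one shift the endpoint by k/45:

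- k = 0: no shift
- k = 1: 1/45 = 2.2 percentage points
- k = 2: 2/45 = 4.4 points
- k = 4: 4/45 = 8.9 points

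If the denominator were the 30 participants used in the sample size calculation, one participant would be worth 1/30 = 3.3 points. The documents give no basis for choosing k.

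**Step 5: scale against sampling error.** Suppose, purely for illustration, 2 participants have clinical events and 2 others have laboratory events only. The exact (Clopper-Pearson) 95% intervals are:

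- clinical only, 2/45 = 4.4% (0.5% to 15.1%)
- combined, 4/45 = 8.9% (2.5% to 21.2%)

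The intervals overlap widely. The issue is what the endpoint counts; the plan sets no decision threshold that such a shift would cross.

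**The case against.** A reader might infer that laboratory toxicities are excluded from the endpoint, that renal and hepatic toxicity would be missed, and that any statement on safety would rest on symptoms alone. The documents do not support this. The endpoint says adverse events, and no sentence excludes laboratory findings. Adverse events are assessed at every visit without restriction to clinical findings. The laboratory values are kept in REDCap and can be graded at analysis. A monitoring committee that includes an HIV clinician, an HIV pharmacologist and the study statistician reviews safety twice, and nothing confines it to symptoms. These points stand.

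The Adverse Events paragraph also breaks off mid-sentence in the available text, and the safety row of Addendum A shows no entries. Both may be effects of reading the PDF, and neither is used here against the plan. They are a reason for some caution in arguing from silence. The two sentences that state the rule are complete, however, and both name signs and symptoms.

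It is also true that the documents do not reproduce the cited grading table, so its laboratory thresholds cannot be checked here, and that a separate laboratory summary would remove much of the ambiguity.

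None of this closes the gap. Storing a value is neither grading it nor counting it, and committee review does not define the reported proportion. The stated rule remains narrower than the endpoint it feeds.

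**Conclusion.** The point holds as a mismatch of scope. Applied literally, the grading and recording rule gives symptomless grade 3 or higher laboratory abnormalities no route into the secondary endpoint, which could therefore under-count laboratory toxicity. It does not follow that such toxicity will go undetected.

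The size is unknown because the documents give no clinical or laboratory event rate. Any projected corrected proportion would rest on invented rates. What can be said is 2.2 percentage points per participant with only a laboratory event, assuming a denominator of 45; if there are none, the endpoint does not move. The primary endpoint is unaffected. The correction should be made because the gap touches the only secondary endpoint and is cheap to close.

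**What to change.** - Reword the grading and recording rule so that it covers all signs, symptoms and laboratory abnormalities of grade 3 or above, and name the tests (CMET and CBC, including creatinine, AST and ALT).
- Grade the results already collected with the grading table the protocol cites, after confirming that it covers each named test.
- Count on-treatment abnormalities that worsen in grade from baseline, so that raised values permitted at entry are not counted as new events.
- Report the endpoint combined, and also separately for clinical and laboratory events, at weeks 24 and 48.

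This takes a short protocol amendment and some programming. It needs no new visits, samples or participants and changes no treatment rule. The downside is that the reported event proportion may be somewhat higher; the separate reporting lets readers see why.

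### Enrolling 45 does not cover ~50% attrition: it leaves about 22 completers, not 30, and a 95% CI width of about 0.40 rather than 0.35

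*Combined protocol and SAP*

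**What the plan says.** The Sample Size Justification rests on the precision of a confidence interval for one proportion, the share of patients suppressed at week 24. It proposes that "this proportion could range from .60 to .80" and admits uncertainty about how many patients will stay on treatment to week 24. Its table gives 95% limits for 20, 25, 30, 35 and 40 patients at proportions of 0.6, 0.7 and 0.8. The table's estimates are "based on the number of patients who complete 24 weeks of therapy", so its sample sizes count completers and not enrolled patients.

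The closing paragraph picks one row, the one for a suppression proportion of 0.70: "A sample size of 30 produces a two-sided 95% confidence interval with a width equal to 0.35". The next sentence moves from completers to enrolment: "The sample size will be increased to 45 patients to account for an estimated attrition of ~50" percent. The Abstract (Interventions/Evaluations) confirms the total: "We plan to enroll 45 participants". No other derivation of 45 appears.

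The primary endpoint (Endpoints, item 1) is the proportion "with HIV RNA <50 copies/mL at week 24 by FDA Snapshot Algorithm". Neither the Sample Size Justification nor the Data analysis section says which patients form the denominator.

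**The concern.** If half of those enrolled are expected to be lost, enrolment must be twice the number of completers wanted. An increase from 30 to 45 is only half as much again, so the enrolment, the attrition rate and the completer target cannot all be right.

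What is at stake is the quantitative case for the trial's size. The study is an estimation pilot and gives no power calculation, so the expected precision is what justifies 45 patients. The row singled out would not be reached under the plan's own attrition assumption. The monitoring committee, which reviews recruitment and futility, would also be working from an expectation of 30 completers that the plan's figures do not support.

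**Working it through.** **Inputs**, all from the Sample Size Justification: 30 completers wanted; two-sided 95% interval; proportion 0.70, with a range of 0.60 to 0.80; attrition d of about 0.50; 45 enrolled.

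**Step 1: reproduce the plan's width.** The Clopper-Pearson limits for x successes in n are the 2.5% quantile of Beta(x, n − x + 1) and the 97.5% quantile of Beta(x + 1, n − x), with x = np. At n = 30, p = 0.70 (x = 21) they are 0.506 and 0.853, a width of 0.347, which matches the stated 0.35 (0.51 to 0.85). All 15 table rows are reproduced to rounding. The Wald (0.328) and Wilson (0.312) widths do not match, so the table uses the exact method.

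**Step 2: enrolment needed.**
- Required: n/(1 − d) = 30/(1 − 0.50) = 60.
- The stated 45 equals n(1 + d) = 30 × 1.5. The plan does not show its calculation, so this origin is an inference.
- Completers from 45: 45 × (1 − 0.50) = 22.5, that is 22 or 23. The shortfall is 30 − 22.5 = 7.5, or 25%.
- Attrition at which 45 suffices: 1 − 30/45 = 0.333.

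**Step 3: precision with 22 or 23 completers** (same exact method).

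| Proportion | Width, n = 30 | Width, n = 22 | Width, n = 23 |
|---|---|---|---|
| 0.60 | 0.367 | 0.428 | 0.419 |
| 0.70 | 0.347 | 0.404 | 0.396 |
| 0.80 | 0.309 | 0.361 | 0.353 |

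At 0.70 and n = 22 the limits are 0.470 to 0.874, so the lower limit drops below one half. The relative widening at 0.70 is 0.404/0.347 = 1.16 for n = 22 and 0.396/0.347 = 1.14 for n = 23. Because np is not whole here (nor is it in the plan's own n = 25 and n = 35 rows at 0.70), whole counts were also checked: 15/22 gives 0.410, 16/22 gives 0.395 and 16/23 gives 0.397. The plan's own rows at 0.70, 0.42 for n = 20 and 0.38 for n = 25, bracket these values.

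**Step 4: does the approximation sign matter?**

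| Attrition | Completers from 45 | Enrolment needed for 30 |
|---|---|---|
| 33.3% | 30.0 | 45 |
| 40% | 27.0 | 50 |
| 45% | 24.8 | 55 |
| 50% | 22.5 | 60 |
| 55% | 20.2 | 67 |

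No rate from 40% to 55% gives 30 completers from 45.

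**Step 5: the other possible denominator.** Assume that all 45 are analysed and that patients without week-24 data count as not suppressed. The exact width is then 0.282 at 0.70 and at most 0.305 at any proportion. With half of the patients lacking data, the observed proportion cannot exceed 0.50. If completers are suppressed at 0.60 to 0.80, the proportion over all 45 is 0.30 to 0.40 (for example 22.5 × 0.70/45 = 0.35).

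**The case against.** The strongest reply is that a Snapshot endpoint would normally keep every enrolled patient in the denominator. Attrition would then lower the estimate and not widen the interval, and precision would be better than promised: 0.282 at 0.70, against 0.35. This limits the harm. The widening to 0.40 applies to a completer analysis, and the plan does not say that the primary analysis is one. It does not rescue the sentence. On an all-enrolled basis no inflation for attrition would be needed, 0.35 would still be the wrong width, and the assumed range of 0.60 to 0.80 could not be reached with half the patients missing. The paragraph makes sense only on the completer basis, where its arithmetic fails.

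A second reply is that the attrition rate carries no time point and follow-up runs to week 48. If half were lost by week 48 at a constant rate (an assumption), the loss by week 24 would be 1 − √0.5 = 29%, leaving about 32 completers and a width of about 0.34. This is possible, but the surrounding sentences speak only of week 24, so it is not the natural reading.

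Third, this is a pilot with no test or decision threshold tied to the width, the table already lets a reader interpolate to about 0.40, and the final interval will be computed from the observed data. All of that is true. It bears on how serious the error is, not on whether it is one.

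**Conclusion.** The concern holds. On the plan's own basis, 45 enrolled with about 50% attrition by week 24 gives 22 or 23 completers, 25% fewer than the 30 on which the stated precision rests. The exact 95% CI width at 0.70 becomes about 0.40 instead of 0.35, a difference of about 0.05, or 14 to 16%. The conclusion assumes that the interval is computed among completers, as the table is, and that the attrition refers to week 24. It is stable for attrition between 40% and 55%. The effect on the trial is moderate: conduct and analysis do not change, and 45 may be a reasonable pilot size. But the justification given for that number is wrong as written.

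**What to change.** First state the denominator of the primary proportion and the time point to which the attrition estimate refers. Then make the figures agree in one of these ways.

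- **Keep 45 and about 50% attrition (preferred).** Replace the last two sentences of the justification with text such as: With 45 enrolled and about 50% attrition by week 24, about 22 patients are expected to complete; the exact 95% CI width is then about 0.40 at a proportion of 0.70. Add n = 22 to the table: 0.43 (0.37 to 0.80) at 0.6, 0.40 (0.47 to 0.87) at 0.7 and 0.36 (0.58 to 0.94) at 0.8.
- **Keep 45 and 30 completers.** Restate the attrition assumption as about 33%, if that is the real expectation.
- **Keep 30 completers and about 50% attrition.** Enrolment would have to be 60. The correction does not require this.

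If the Snapshot analysis is to include all 45, report the precision for n = 45 (0.282 at 0.70, at most 0.305) and set the assumed range of proportions with missing patients counted as not suppressed.

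Under the preferred option the cost is two sentences and a short table addition, plus the statement of denominator and time point. No patients are added; the stated precision becomes slightly less favourable.
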